Study Title	Adaptive Prediction of Antimicrobial Susceptibility and its Implementation to Improve the Management of Urinary Tract Infection
Internal ref. no. (or short title)	ADAPT-AST (Adaptive Antimicrobial Susceptibility Testing)

Study Design	Retrospective observational study
Study Participants	Demographic, antimicrobial prescribing and microbiology specimen data from patients >18 years in the catchment area served by Liverpool University Hospitals NHS Foundation Trust and Liverpool Community Health
Planned Size of Sample (if applicable)	> 250,000 specimens estimated (the number of patients will be fewer because some patients will have had more than one specimen sent)
Outcomes	
Primary outcome:
 
The number of antimicrobial susceptibility results that 'should' spur action by a clinician on the day that actual first-line AST results were reported (in green on Figure 5).
 
Secondary outcomes:
 
 
1. The number of days until a result that 'should' spur action by a clinician (in green on Figure 5).
 
2. The number of antimicrobial susceptibility results that 'could' spur action by a clinician on the day that actual first-line AST results were reported (in yellow on Figure 5).
 
3. The number of days until a result that 'could' spur action by a clinician (in yellow on Figure 5).
 
4. The projected health economic cost per specimen, including laboratory (e.g., consumable cost) and patient (e.g., drug toxicity, clinical failure) measures guided by the above criteria.
 

Follow up duration (if applicable)	Not applicable
Planned Study Period	3 years
Project Question/Aim(s)	
 
1. Can causal, explainable Bayesian causal inference (BCI) approaches be used to develop/(re)validate (train/test) clinical prediction models for prediction of urine organism antimicrobial susceptibility using NHS care data?
 

	2. Can the resulting ADAPT-AST adaptive, informatics-based (data-driven and system-wide) approach target AST for UTI better than existing approaches can, thereby improving timeliness of clinical decision making and saving resources through efficiency?
--	---

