### **3.1.3 Sample size**

The main sample size consideration is the volume of data required to train the BCI algorithm; this will be higher than the sample size required to provide 80% power to detect a significant (e.g.,  $p < 0.05$ ) difference between groups in the simulated interventional study. For the binary LR techniques like that used to develop the predictive model, however, much larger sample sizes are required to provide predictive accuracy(43). Given that a range of BCI techniques are likely to be trialled and that most of the variation will be taking place in a small proportion of samples, data pertaining to a large number of specimens will be required. All eligible patients who have grown an organism in a urine specimen during the a five year period from 17th May 2017 will be recruited for the development and testing of the predictive algorithm. This period has been chosen to provide a balance between strength of model, the amount of data available, computational power required and 'concept drift' i.e., changes in susceptibility patterns and laboratory practice over time; the most recent AST practice change in LCL was implemented 17th May 2017(44). This period will provide an estimated sample size of at least 250,000 specimens, which will pertain to fewer patients than that number as some will have had urine specimens sent more than once.

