### **3.3.3 Statistical Analysis**

A chi square goodness of fit test will be conducted to determine whether the counts of, and number of days until, 'should' and 'could' action results follow a Poisson distribution; if so, a one-sample exact Poisson test will be run to determine whether the mean number of 'should' and 'could' action results per specimen and the number of days to these results using ADAPT-AST would be different from the expected number using the LCL SOP. The mean financial cost per specimen will be analysed either with a single-sample paired t-test or Wilcoxon signed-ranks test depending on whether the data are normally distributed.

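### The tests in Section 3.3.3 treat specimens as independent although patients contribute several: cost p-values are likely too small, and the primary outcome's error rate is uncontrolled

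*Protocol*

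**What the plan says.** Section 3.3.3 sets out three steps.

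- **Gate:** "A chi square goodness of fit test will be conducted to determine whether the counts of, and number of days until" results of either kind ('should' or 'could') are Poisson distributed.
- **Counts and days, only if the gate is passed:** "a one-sample exact Poisson test will be run to determine whether the mean number of" such results per specimen, and the days to them, "would be different from the expected number using the LCL SOP".
- **Cost:** "The mean financial cost per specimen will be analysed either with a single-sample paired t-test or Wilcoxon signed-ranks test", the choice depending on normality.

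Section 3.1.3 gives the size of the data: "This period will provide an estimated sample size of at least 250,000 specimens". It then describes this as a total "which will pertain to fewer patients than that number as some will have had urine specimens sent more than once". The Study Summary agrees: "the number of patients will be fewer because some patients will have had more than one specimen sent".

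Section 3.2.1 draws the 80% training set at random by specimen, and Section 3.3.1 evaluates ADAPT-AST on the remaining 20%. Section 3.3.2 applies both the ADAPT-AST and the SOP algorithm to each specimen. No section mentions a patient-level term, clustered variance, resampling by patient or a rule of one specimen per patient. The limitations in Section 3.3.4 do not raise the matter.

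**The concern.** A goodness-of-fit test, an exact Poisson test, a paired t-test and a signed-ranks test all need independent units. The protocol names them with the specimen as the unit and also states that patients repeat. This goes beyond detail left to a later analysis plan: the named tests rest on an assumption that the protocol's own text contradicts.

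The protocol also gives reasons to expect correlation. Section 3.1.2 treats earlier colonisation with a resistant organism as a risk factor for later resistant infection. Section 3.2.1 predicts from the patient's prior data. Section 3.3.2 scores results against allergies, renal function and drug interactions, which tend to persist in a patient. If history predicts susceptibility, repeat specimens from one patient resemble each other. Patients with many specimens are then counted as more independent evidence than they provide.

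At stake is the validity of the p-values for the primary outcome, the 'could' and days outcomes, and cost.

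**Working it through.** **Inputs from the protocol.** At least 250,000 specimens (3.1.3); a random 20% by specimen for evaluation (3.2.1, 3.3.1); both algorithms on each specimen (3.3.2). The 250,000 is the expected yield of a five-year window, with no effect size or variance behind it, so there is no power formula to reproduce. What follows from it is 0.20 × 250,000 = 50,000 evaluation specimens.

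**Assumed, because the documents give no value.**
- m_w: size-weighted number of specimens per patient in the full data
- ICC: within-patient correlation of the paired ADAPT-AST minus SOP difference
- φ: variance/mean ratio of the counts
- ρ: within-specimen correlation of the ADAPT-AST and SOP counts

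**Step 1: cost.** A sampled specimen has on average 0.2 × (m_w − 1) other specimens from the same patient in the 20% sample. Hence

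DE = 1 + ICC × 0.2 × (m_w − 1), and true α = 2[1 − Φ(1.96/√DE)] at nominal 0.05.

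| m_w | ICC | DE | SE factor | True α | Effective n of 50,000 |
|---|---|---|---|---|---|
| 2 | 0.1 | 1.02 | 1.01 | 0.052 | 49,020 |
| 3 | 0.3 | 1.12 | 1.06 | 0.064 | 44,643 |
| 5 | 0.5 | 1.40 | 1.18 | 0.098 | 35,714 |

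A more extreme case, m_w = 10 with ICC = 0.5, gives DE 1.90 and α 0.155.

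**Step 2: counts and days.** Section 3.3.3 does not say how the SOP expected number is obtained. I take it from the same specimens, as Section 3.3.2 implies. The test uses a variance of n × mean. The true variance of the ADAPT-AST minus SOP total, with equal variances in the two arms, is n × 2φ × mean × (1 − ρ) × DE. The ratio is

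R = 2φ(1 − ρ) × DE, and true α = 2[1 − Φ(1.96/√R)].

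With φ = 1, the case in which the gate should let the test run, true α is:

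| ρ | DE 1.00 | DE 1.12 | DE 1.40 |
|---|---|---|---|
| 0 | 0.166 | 0.190 | 0.242 |
| 0.5 | 0.050 | 0.064 | 0.098 |
| 0.7 | 0.011 | 0.017 | 0.033 |
| 0.9 | <0.001 | <0.001 | <0.001 |

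The test is anti-conservative only if 2(1 − ρ) × DE > 1. That means ρ below 0.50, 0.55 and 0.64 for the three columns. Clustering raises α in each row where it is not already negligible, but ρ decides which side of 0.05 the test falls.

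**Step 3: simulation check.** The set-up was 3,000 patients, geometric cluster sizes with mean 2.5, a 20% sample by specimen, and 1,500 runs per setting. Without a patient effect, the paired t-test rejected in 4.5% to 5.5% of runs; with one, in 5.1% to 10.7%. With a patient effect, the Poisson test rejected in 38% to 52% of runs when the arms shared no component (ρ then negative), in 4% to 7% at ρ about 0.56 to 0.63, and in none at ρ about 0.88 to 0.89.

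**Step 4: practical size.** With 50,000 specimens and an assumed mean of 1 to 3 results per specimen, the nominal one-sample Poisson test has 80% power at a difference of (1.96 + 0.84) × √(mean/50,000). That is 0.0125 to 0.0217 results, or 1.25% to 0.72% of the mean. Multiplying by √1.40 = 1.18 moves this to about 1.5% to 0.9%.

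**The case against.** The strongest case against has four parts.

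1. **Direction for the primary outcome.** A reader might infer that clustering makes the primary p-value too small. The documents do not support that. The named test does not analyse differences, so a design-effect formula that presumes a test calibrated before clustering does not apply. Two panels scored on the same specimen and patient are plausibly positively correlated, and at ρ = 0.7 the test is conservative even at DE 1.40. This stands. Nor can one speak of intervals being too narrow, because Section 3.3.3 specifies none.

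2. **Conditional test.** The Poisson test runs only if the gate is passed. With about 50,000 specimens and counts capped by a 7-result panel, the gate may well fail, and no alternative test is then named. This also stands. It does not rescue the plan, because the gate assumes independent specimens too.

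3. **Size.** A reader might infer error rates of a quarter or more. Those need whole patients in the evaluation set: DE = 1 + ICC × (m_w − 1) = 3.0 at m_w = 5 and ICC = 0.5, so α is about 0.26. Section 3.2.1 splits by specimen, which thins the clusters and keeps the inflation modest. One might also suppose that repeat specimens usually receive the same ADAPT-AST panel. The protocol does not say so, and panels depend on predictions from a window before each specimen.

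4. **Consequence.** This is a retrospective simulation. Section 3.3.4 requires randomised studies before deployment, and the cost-effectiveness conclusion in Section 3.4 rests on ICERs and sensitivity analyses, not on the cost p-value. This argues for a lower priority, but it does not make the named tests valid.

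**Conclusion.** The point holds as a should-fix. The tests in Section 3.3.3 assume independent specimens, the protocol says that they are not all from different patients, and nothing adjusts for it.

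- **Cost:** p-values are too small whenever the paired differences are positively correlated within patients, which is plausible from Section 3.1.2 but not quantified. For 2 to 5 specimens per patient (size-weighted) and a correlation of 0.1 to 0.5, a nominal 5% test has a true rate of about 5% to 10%.
- **Primary, 'could' and days outcomes:** clustering inflates the true variance, but the ignored pairing and the fixed SOP mean also act, and can outweigh it. The error rate is uncontrolled and its net direction is unknown.
- **Practical effect:** point estimates are unaffected, and at about 50,000 specimens only conclusions about small differences would change.

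The sizes rest on assumed cluster sizes and correlations. The presence of the problem rests on the protocol's text alone.

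**What to change.** In Section 3.3.3, replace the named tests with one analysis for counts, days and cost: the per-specimen paired difference, ADAPT-AST minus SOP, with 95% confidence intervals and p-values from a patient-level cluster bootstrap or patient-clustered robust standard errors. Name the pseudonymised study number in Table 1 as the cluster identifier. This repairs the clustering and the ignored pairing together, and it removes the dependence on the Poisson gate.

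The cost is a short change to the text and a few lines of code, with no new data. Uncertainty for cost becomes somewhat wider: a standard error factor of about 1.01 to 1.18 under the assumptions above. For counts and days, uncertainty may widen or narrow, depending on how strongly the two panels' results agree within a specimen.

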## ADAPT-AST Protocol

[figure not shown]

Figure 1: Current laboratory workflows fail to make use of past information related to the patient or the patient's immediate environment to make decisions about susceptibility testing, which may lead to delays in appropriate decision making. In low prevalence AMR settings, testing contributes little to clinical care.

[figure not shown]

Figure 2: In highly-prevalent AMR settings, a second round of susceptibility testing is required before appropriate antimicrobials are identified and therapy is changed. Each additional panel of susceptibility testing typically incurs at least 24 hours of delay.

This standard practice results in the provision of susceptibility information for clinicians which is:

a) Imprecise

Some laboratories in high income settings can test very large panels of antimicrobials immediately at day one (for example, the ThermoFisher® Sensititre™ Gram Negative MIC Plate tests 22 antimicrobials), but more commonly, and particularly in low or middle income (LMIC) settings, a selected subset of antimicrobials is tested at day one to save resources (for example, the MAST URI® system used in Liverpool Clinical Laboratories [LCL] tests a 7-antimicrobial panel) (4–6). There is currently a ‘one-size-fits-all’ approach to this testing, where a standard panel of antimicrobials are initially tested against urinary pathogens. These panels do not adapt for previous resistance patterns, antimicrobial prescribing, or demographic information despite their potential impact on the likelihood of susceptibility to various agents(7).

b) Inefficient

When the standard panel tested yields no appropriate antibiotics for the clinician to use, a ‘second line’ standard panel of antibiotics will then be tested. This process unnecessarily consumes the time of laboratory staff and requires additional resources to those used to set up the initial unusable panel of antimicrobials. Lack of information related to appropriate oral or outpatient parenteral antimicrobial therapy (OPAT) treatment options delays early discharge with patients required to stay in hospital to receive high-frequency intravenous (IV) antibiotic regimens(8).

c) Inequitable

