## **3.3 Development and Clinical Evaluation of ADAPT-AST in a simulated clinical setting**

### **3.3.1 AST Decision Making Algorithm Development**

The final stage of the project will be evaluating the potential clinical and resource impact of the testing framework on the same 20% of samples used in the testing dataset above. To do this, a clinically suitable AST decision making model first will need to be developed. Comparison of a range of algorithmic approaches is likely to be required, but the aim of the first decision model trialled will be to select 7 antimicrobials for testing (the number in the standard first-line panel currently tested under existing LCL SOPs). The antimicrobials that will be initially eligible for AST selection are those for which probability calculations will be outputted, listed above in Table 2.

The first prioritisation approach trialled will be to rank antimicrobial choices in descending order of susceptibility uncertainty except for cefpodoxime and cefoxitin, then to apply an algorithm in Figure 4 to ensure that a mixture of oral and intravenous agents is tested.

[figure not shown]

Figure 4: Algorithm used to select 7 antimicrobials from the sorted shortlist.

\*Amoxicillin, Amoxicillin-Clavulanate, Aztreonam, Cefalexin, Ceftazidime, Phenoxycephalothin, Piperacillin-tazobactam.

Cefpodoxime or cefoxitin are not used as treatments in the local area, but resistance to either antimicrobial indicates a high probability of resistance mechanisms which preclude use of some beta lactams (BL) and beta-lactam-beta-lactamase-inhibitor combinations (BL-BLIC)(57,58). Therefore, the algorithm will also be designed for cefpodoxime and cefoxitin to only be tested when their susceptibility is sufficiently uncertain (a defined classification threshold will be calculated for this) and there is a chance of the affected BLs / BL-BLICs, cefpodoxime and cefoxitin all being tested as part of the panel of 7.

No additional weighting, ranking or exclusion criteria will initially be applied, but depending on evaluation based on a priori microbiology / clinical / health economic knowledge, measures may need to be taken to further steward the AST choices. These may include exclusion of certain antimicrobial choices which are less practically useful for UTI but for which resistance uncertainty may be high (e.g., teicoplanin) or algorithmic prioritisation/exclusion/weighting measures for factors such as WHO

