### **3.3.2 Outcomes**

Outcomes will be assessed and compared between the 7-result AST panels provided by ADAPT-AST algorithms and those provided by standard of care algorithms based on LCL current SOPs as of 2023, both of which will be run on every available specimen. Susceptibility information will be assessed alongside drug allergies, renal function, drug interactions to characterise results that 'should', 'could', and cannot be actioned by the clinician. Computer algorithms will be written to perform this assessment in line with the schema in Figure 5 (amoxicillin provided as an example).

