### Secondary outcomes:

5. The number of days until a result that 'should' spur action by a clinician (in green on Figure 5).
6. The number of antimicrobial susceptibility results that 'could' spur action by a clinician on the day that actual first-line AST results were reported (in yellow on Figure 5).
7. The number of days until a result that 'could' spur action by a clinician (in yellow on Figure 5).

8. The projected health economic cost per specimen, including laboratory (e.g., consumable cost) and patient (e.g., drug toxicity, clinical failure) measures guided by the above criteria.

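### Section 3.3.3 names the mean cost per specimen as the target, then lets a normality check switch to a Wilcoxon test that does not address the mean unless paired differences are symmetric

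*Protocol*

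**What the plan says.** The last secondary outcome (section 3.3.2) is "The projected health economic cost per specimen, including laboratory (e.g., consumable cost) and patient (e.g., drug toxicity, clinical failure) measures". Section 3.3.2 also says that ADAPT-AST and the laboratory's standard procedure are compared on the same specimens, "both of which will be run on every available specimen", so each specimen gives one paired cost difference.

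For the analysis, section 3.3.3 names the quantity, "The mean financial cost per specimen", and continues that it "will be analysed either with a single-sample paired t-test or Wilcoxon signed-ranks test depending on whether the data are normally distributed". It sets no symmetry condition for the Wilcoxon branch and asks for no separate estimate of the mean difference if that branch is taken.

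The evaluation uses "the same 20% of samples used in the testing dataset above" (section 3.3.1). Section 3.1.3 expects at least 250,000 specimens and notes that, among patients, "some will have had urine specimens sent more than once".

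**The concern.** The sentence fixes a target and then allows a test of something else. A paired t-test concerns the mean of the paired differences. A signed-rank test concerns their pseudomedian, which equals the mean under symmetry but generally not otherwise. Normality therefore does more than choose between two routes to one answer: it can change the question.

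The documents make asymmetry plausible without establishing it:

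- The outcome counts toxicity and clinical failure, which can be costly in a few patients.
- Section 1.1 says that a second panel follows when the first yields nothing usable, and that this "requires additional resources to those used to set up the initial unusable panel of antimicrobials". Such costs fall on some specimens and not on others.
- Section 3.1.3 expects that "most of the variation will be taking place in a small proportion of samples". That remark concerns the modelling data and not costs, so it is weak support.

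At stake is the sign of the cost result. Wilcoxon could favour the strategy that is dearer on average, or hide a real mean saving. Saving resources is part of the second project question (section 2).

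**Working it through.** The protocol states no figure to reproduce here: it gives no cost, standard deviation or effect size. All cost values below are assumptions, and tests are taken as two-sided at 5%.

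**Number of pairs.** n = 0.20 × 250,000 = 50,000 (sections 3.1.3 and 3.3.1).

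**Which branch is taken, if a formal normality test is used.** The approximate 5% cut-off for sample skewness is 1.96 × √(6/50,000) = 0.021. In repeated simulations at n = 50,000, D'Agostino's test rejected in 80% to 85% of runs at a true skewness of 0.035, in 98% or more at 0.05 and in 100% at 0.07. Skewness this small is of no practical importance, yet it would send the analysis to Wilcoxon.

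**When the two tests disagree in direction.** Let a share 1 − p of the non-zero differences equal s in one direction and a share p equal k × s in the other, with k > 1. The minority then holds the top ranks:

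- Minority rank sum ≈ (n²/2)(1 − (1 − p)²); majority rank sum ≈ (n²/2)(1 − p)². They are equal at p = 1 − 1/√2 = 0.293, whatever k is.
- Mean, in units of s and signed towards the minority, = pk − (1 − p). It changes sign at p = 1/(1 + k).

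The mean and Wilcoxon therefore oppose each other for p between 1/(1 + k) and 29.3%: 16.7% to 29.3% at k = 5, 9.1% to 29.3% at k = 10, and 2.4% to 29.3% at k = 40. With n²/2 = 1,250 million:

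| k | p | Mean (units of s) | Minority rank sum | Majority rank sum | Direction |
|---|---|---|---|---|---|
| 5 | 0.20 | 1.00 − 0.80 = +0.20 | 450M | 800M | opposed |
| 10 | 0.15 | 1.50 − 0.85 = +0.65 | 347M | 903M | opposed |
| 10 | 0.05 | 0.50 − 0.95 = −0.45 | 122M | 1,128M | agree |
| 40 | 0.05 | 2.00 − 0.95 = +1.05 | 122M | 1,128M | opposed |
| 40 | 0.01 | 0.40 − 0.99 = −0.59 | 25M | 1,225M | agree |
| 40 | 0.31 | 12.40 − 0.69 = +11.71 | 655M | 595M | agree |

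**A simulated data set with spread.** n = 50,000, difference = ADAPT-AST minus standard. For 95% of specimens the difference is normal with mean +0.5 and SD 0.3; for 5% it is minus a gamma variable with shape 2 and mean 20. Some of the normal draws fall below zero, so about 90.5% of specimens are actually dearer.

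- Expected mean: 0.95 × 0.5 − 0.05 × 20 = −0.525. Simulated: −0.52 (95% CI −0.57 to −0.47), a saving.
- Rank sums: 1,118 million for dearer against 132 million for cheaper. Under the null each is about 625 million with SD about √(n³/12) = 3.2 million, so Wilcoxon would declare ADAPT-AST dearer decisively.
- The mirror case gave a mean of +0.49 (0.44 to 0.54) with the rank sums reversed.
- With symmetric normal differences (mean 0.05, SD 3) the two directions agreed in 500 of 500 runs.

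**False rejection when the true mean difference is exactly zero, n = 50,000, 200 runs each.**

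| Shape of differences | Wilcoxon rejects | Paired t rejects |
|---|---|---|
| Symmetric, t with 5 df | 7.5% | 6.0% |
| Gamma, skewness 0.1 | 49% | 4.5% |
| Gamma, skewness 0.4 | 100% | 3.5% |
| Lognormal, sigma 0.5 | 100% | 7.0% |
| Lognormal, sigma 1 | 100% | 2.5% |
| Large saving in 5% of specimens | 100% | 3.5% |
| Large saving in 20% of specimens | 100% | 2.5% |

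Simulation error around 5% is about ±3 points, so the t-test is at its nominal level throughout. A separate run at skewness 0.1 put Wilcoxon at about 41%.

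**Whether normality is needed.** In four skewed scenarios (2,000 runs each, independent specimens) the t-based 95% interval covered the true mean in 94.9% to 95.4% of runs. The standardised mean difference detectable with 80% power is (1.960 + 0.842)/√50,000 = 0.0125. Non-normality is thus no reason to leave the mean at this size.

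**The case against.** The strongest reply has four parts.

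1. **The trigger is not certain.** The protocol does not say how normality is judged. That may be set in a statistical analysis plan, and a graphical check need not lead to Wilcoxon. This stands: the claim about the likely branch holds only for a formal test. The mismatch itself does not depend on it, because the protocol already fixes the target, both tests and the rule for choosing.

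2. **The reversal needs a particular cost pattern.** Both strategies test seven antimicrobials, so many laboratory differences could be exactly zero. Standard Wilcoxon drops zeros, and if the remaining differences share a sign, the two tests agree. This also stands: p in the working is a share of the non-zero differences, and reversal is a possibility, not a forecast. In addition, section 3.3.3 says financial cost where the outcome says health economic cost. If only laboratory costs were meant, the toxicity and failure costs would not contribute to skewness.

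3. **The consequence is small.** This is the last of four secondary outcomes in a retrospective simulation. Cost-effectiveness is judged by the separate decision model in section 3.4, and section 3.3.4 calls for randomised studies before deployment. Nothing says the mean would go unreported beside a Wilcoxon p-value. This limits the weight of the point but does not remove it, since section 3.4 leaves the test in 3.3.3 unchanged.

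4. **Clustering by patient is a different matter.** True: removing the normality condition is justified without it. It belongs in the replacement sentence because any interval for the mean must reflect repeat specimens.

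**Conclusion.** The concern holds. Section 3.3.3 names a mean and allows a test that does not address the mean unless paired differences are symmetric. This is an error in what the protocol fixes, not a detail left for later.

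Its size depends on costs the protocol does not give. Under symmetry there is no reversal. Under the assumed asymmetric patterns, Wilcoxon rejects a true zero mean difference in about 41% to 49% of runs at a skewness of 0.1 and in all runs at 0.4, and it can contradict a clear mean saving. Reversal requires a minority share inside the windows shown, and the probable switch to Wilcoxon assumes a formal normality test on about 50,000 pairs.

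The effect is confined to the secondary cost outcome; the primary outcome and the decision model are untouched. The text should be changed, since the switch gains nothing at this sample size.

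**What to change.** In section 3.3.3, remove the normality condition and state that, whatever the distribution, the analysis estimates the mean paired difference in cost per specimen (ADAPT-AST minus standard procedure) with a 95% confidence interval. The interval should be either t-based with standard errors clustered by patient, or from a bootstrap that resamples patients, because some patients contribute several specimens. Wilcoxon may stay as a descriptive result, not as the test of the mean.

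The cost is one sentence. No new data are needed, and the pseudonymised study number already planned in section 3.1.2 identifies specimens from the same patient.
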